2.2. Specific objectives

- To describe demographic, medical history, gynecologic and obstetric history of the studied population.
- To describe the analgesic strategies and drugs used for pain relief in primary dysmenorrhea in the studied population.
- To evaluate the quantified perception of usual pain in primary dysmenorrhea using a VAS in college students 18 years or older.
- To explore if a difference exist in the acute quantified perception of pain in primary dysmenorrhea, using a VAS, among 18-year or older college students prior to receive the music or silence interventions.
- To evaluate if a difference exist in the acute quantified perception of pain in primary dysmenorrhea, using a VAS, among 18-year or older college students after receiving the music or silence interventions.
- To explore if a difference exist in the change of quantified pain perception using a VAS in primary dysmenorrhea, from the moment prior to the intervention until the moment after the intervention, among 18-year or older college students that listened to music or stayed in silence.
- To evaluate if a difference exist in the acute quantified perception of pain in primary dysmenorrhea, using a VAS, among 18-year or older college students 3 to 6 hours after receiving the music or silence interventions
- To explore if a difference exist in the change of quantified anxiety in primary dysmenorrhea, evaluated with the Zung's scale, from the moment prior to the intervention until the moment after the intervention, among 18-year or older college student that listened to music or stayed in silence.
- To evaluate if a difference exist in requirements of pharmacological analgesics for pain relief in primary dysmenorrhea, among college students that received music compared to those that stayed in silence after the intervention, and 3 to 6 hours after the intervention.
- To evaluate if differences exist in heart rate, systolic blood pressure, and diastolic blood pressure, using a calibrated digital sphygmomanometer, between 18-year or older college students receiving music and those staying in silence.

3. Material and Methods

Design

A prospective and single blinded randomized clinical trial will be conducted. Two groups will be compared, the experimental group will receive a music intervention, and control group will stay under the same condition and the same time with headphones in silence.

Study population

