Female students 18 years or older matriculated to one of the programs registered at the School of Medicine and Health Sciences from Universidad del Rosario. Students volunteering to participate, those giving written consent to participate in this protocol, and those complying our eligibility criteria:

- Inclusion criteria
 1. Students at least 18 years old.

2. With legal and cognitive capacity to give written consent to participate.
3. Patients that comply to characteristics and definition of primary dysmenorrhea according to literature (2, 4-8):
 - a. Crampy-like pain located in the inferior abdomen, lumbar region, or inguinal region
 - b. Pain initiating no longer than 24 hours prior to the first bleeding during the menstrual cycle
 - c. Pain lasting 24-72 hours
 - d. Pain that always occurs with menses
4. Ability to understand and respond all questionnaires and measuring tools.

- Exclusion criteria
 1. Prior diagnosis of endometriosis, adenomiosis, myomatous uterus, or any other gynecologic cause of secondary dysmenorrhea.
 2. Any degree of hearing impairment or use of auxiliary hearing devices.
 3. Diagnosed cognitive deficit or neurologic condition.
 4. Prior diagnosis of psychiatric disease, use of anxiolytic or anti-depressive drugs, or history of substance or alcohol abuse in the last two years.
 5. Diagnosis of cancer, diabetes mellitus, or cardiac disease.
 6. Advanced music training (receiving advanced music theory in addition to normal music education given by schools).
 7. Irregular menstrual cycles.
 8. Diagnosis of any endocrine disease.
 9. Current use, or use in the last two months, of oral contraceptive or other hormonal contraceptive method.
 10. Prior gestation or labor.

Variables and measurement tools:

- **Demographic data:** age, current studying semester, religion, and civil status will be collected.
- **Medical history:** medical, surgical and obstetric history will be collected.
- **Menstrual cycle data:** the following will be collected: 1. Menarche; 2. Time between each cycle; 3. Menses duration; 4. Contraceptives use.
- **Pain associated to menses:** using a visual analogue scale (VAS), the usual pain associated to menses will be collected. The VAS uses a 10 cm line that goes from 0 “I have never felt pain during my menses” to 10 “I always feel the worst of pain of my life during menses”.

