5. Did you take any drug for pain relief during your last menses? YES NO

Drug name: _____

Used doses (Number of tablets): _____

E.g. Ibuprophen 4 tablets of 800 mg

6. Did you use any form of non-pharmacological strategy for pain relief during your last menses? YES NO

Specify: _____

For this part please read carefully instructions

Visual analog scale (VAS) consist of a 10 cm line. The line is marked with a 0 in one side and 10 in the other, and consider 0 as the least possible intensity and 10 as the greatest. For using the tool you have to put a mark that represents the perceived intensity that better answers the question.

7. Consider 0 (I have never felt pain during menses) and 10 (I always feel my worst kind of pain). Which is your usual pain associated to menses?

SUPPLEMENT 4. Questionnaire for the day of the intervention

STUDIED VARIABLES

The following document will be of exclusive use for the researchers during the day that the study is conducted. TIME: _____

Please answer the following questions.

1. With a single mark please answer. How much pain are you feeling right now? Consider 0 as "I'm not feeling any pain" y 10 "I'm feeling the worst pain of my life" (patient must answer by herself).

0  10

2. Please answer the following questions with: Never, Sometimes, Most of the time o Always.

Question	Never	Sometimes	Most of the time	Always
Have you felt nervous or anxious lately				
Have you felt fearful lately				
Have you been irritated or have you panicked easily				
Have you felt down				
Have you felt tremulous				
Have you felt headache, pain on your back, or pain on your neck				
Have you felt weak and fatigue easily				
Have you felt palpitations or elevated heart rate				
Have you felt dizzy lately				
Have you felt nausea or stomach disturbances lately				

3. Answer Yes or No. Would you take an analgesic drug or other would you do another analgesic strategy at this moment? If Yes, please specify:

4. At this moment how much time have you felt pain?

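### The usual-pain scale (VAS1) has anchors that mix how often pain occurs with how strong it is and conflict with the form's own intensity instruction, so the descriptive usual-pain objective is measured with ambiguous wording

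*Combined protocol and SAP*

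**What the plan says.** Section 2.2 (Specific objectives) includes a descriptive aim: "To evaluate the quantified perception of usual pain in primary dysmenorrhea using a VAS". VAS1 is the only instrument that serves it.

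The wording of VAS1 appears in two places:

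- **Variables and measurement tools, entry on pain associated to menses:** 0 is "I have never felt pain during my menses" and 10 is "I always feel the worst of pain of my life during menses".
- **Supplement 2, item 7 (the participant form):** "Consider 0 (I have never felt pain during menses) and 10 (I always feel my worst kind of pain", followed by the question "Which is your usual pain associated to menses".

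Directly before item 7, the form gives a general instruction for the line: "consider 0 as the least possible intensity and 10 as the greatest". It asks the participant to "put a mark that represents the perceived intensity that better answers the question".

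Inclusion criterion 3d requires "Pain that always occurs with menses".

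The acute-pain scale used for VAS2 to VAS4 is anchored differently, in the Variables section and in Supplements 4 and 5. It runs from no pain at this moment to the worst pain of the participant's life, with no reference to frequency.

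**The concern.** A visual analogue scale gives an interpretable number only if its two ends bound one attribute. Here the lower end is a statement about history (pain has never occurred), and the upper end is a statement about both regularity and strength. A mark in the middle could mean moderate pain at every menses, or very severe pain at some menses and less at others.

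The form adds a second difficulty. It defines the ends of the line by intensity and then, for the item itself, redefines the same ends with never and always. Nothing says which definition governs.

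At stake is the meaning of the mean usual-pain score, which is a stated objective. So is any informal reading of that score beside the acute scores, which are also on a 0 to 10 line but with other anchors.

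**Working it through.** No formula applies to the wording, so the places are set side by side. The plan's only design calculation is then reproduced to see how far the point reaches.

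1. **Ends of the line in the protocol text.** Lower end: a frequency or history statement. Upper end: frequency (always) and intensity (worst) together. The two ends differ on two attributes.

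2. **Ends of the line on the form.** The general instruction defines 0 and 10 as least and greatest intensity. Item 7 then defines them as never having felt pain and always feeling the worst kind. One page therefore carries two definitions. A participant may use either, and the recorded mark does not show which.

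3. **Text against form.** The protocol's upper anchor refers to the worst pain of the participant's life. The form's refers to her worst kind of pain, without the lifetime reference, and could be read as her worst menstrual pain. These are different reference points.

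4. **How much frequency can vary.** Under criterion 3d every eligible woman has pain with each menses, so how often any pain occurs is fixed by design. What can still vary is how often the pain is at its worst. A woman with fairly severe pain every cycle and one whose pain is at its worst only in some cycles could mark the same point. The screening form (Supplement 1) asks whether cramp-like menstrual pain is present but not whether it always accompanies menses, so some intermittent sufferers could pass that form.

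5. **VAS1 against VAS2 to VAS4.** The acute scale is anchored by intensity only. VAS1 and the acute scores therefore do not share a scale, although both run from 0 to 10.

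6. **Reach into the primary analysis.** The hypotheses under Sample calculation are written in VAS2 and VAS3 only. That section's inputs are allocation ratio 1, z values 2.33 and 1.28, σ = 2 and Δ = 1.5:

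   n = 2 × (2.33 + 1.28)² × 2² / 1.5² = 2 × 13.0321 × 4 / 2.25 = 46.34, rounded up to 47 per group.

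   This matches the plan. VAS1 supplies none of the inputs. The value σ = 2 equals the SD of 2.0 reported from the earlier survey at the same school, whose anchors the documents do not give. Rewording VAS1 leaves 47 per group unchanged.

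**The case against.** The strongest reply is that the form already asks for the right quantity. Its instruction speaks of intensity, it asks for a mark of perceived intensity, and the question asks for usual pain. Criterion 3d largely removes variation in how often pain occurs. The text-to-form difference is slight and may come from translation, since the file has Spanish remnants. No objective, hypothesis or analysis compares VAS1 with VAS2 to VAS4.

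Much of this stands, and it rules out several stronger readings that a reader might infer:

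- **That usual pain is not measured at all, or that the mean carries no intensity information.** The instruction and the question contradict this. The objective is measured, but with conflicting wording.
- **That the scale fails because criterion 3d makes its zero unreachable.** Eligibility criteria often exclude the floor of a scale, and a plain no-pain zero for usual menses would be just as unreachable. The weakness is what this zero means: a history, not an absence of pain.
- **That constant mild pain and occasional severe pain are freely confused.** For eligible women only the frequency of the worst pain is left to vary.
- **That the efficacy result is affected.** The primary endpoint does not use VAS1.

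The reply does not remove the conflict on the form. An instruction that defines the ends one way does not settle the matter when the item below it defines them another way.

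**Conclusion.** The point holds as a minor one about wording. The VAS1 anchors combine frequency with intensity, contradict the form's own definition of the line, and differ at the upper end between protocol and form. The usual-pain objective is therefore measured ambiguously.

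The ambiguity applies to every VAS1 value. The direction and size of any shift in the mean cannot be derived from the documents, because they do not show how many participants would follow each definition.

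The definition of the primary endpoint, its hypotheses and the sample size are unaffected. One assumption should be stated: the Data analyses section does not name the MANCOVA covariates, so a role for VAS1 there can be neither confirmed nor excluded. VAS1 is collected before the intervention, so as a covariate its ambiguous wording would cost some precision but would not bias the randomised comparison.

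**What to change.** In the Variables section and in Supplement 2, item 7, use one identical set of intensity-only anchors tied to a usual menses. For example: *How intense is your pain during a usual menses?*, with 0 = *no pain during my usual menses* and 10 = *the worst pain of my life*. If frequency is of interest, ask it as a separate question.

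The VAS2 anchors should not simply be copied across. Under Procedure, VAS1 and VAS2 are taken in the same session after menstrual pain has begun, and a present-tense zero would invite a rating of current pain instead of usual pain.

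The cost is one line in the text and one on the form. The small downside is a possible loss of continuity with the earlier survey at the same school; whether VAS1 follows that survey's wording cannot be known from the documents.

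The notes added to the protocol indicate that the trial has been run. If VAS1 data are already collected, report the exact anchors used, state the limitation, and do not present the mean as a pure intensity on the same scale as VAS2 to VAS4.

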The study will be explained in detail to the students that are found to be eligible. A speech will be design prior to enrollment to avoid disclosing different information among participants. The speech will mention that: "...they will participate in a research about the effects of music in primary dysmenorrhea, in which they will be compared to a control group..."¹. The speech will explain the rest of the details for the experimental part of the study. Finally, they will be requested to sign informed consent for participation.

After signing informed consent, patients will be allocated by computer generated randomization. Randomized codes will be generated and information about the study will be put in envelops. The information inside the envelope will not disclose the allocated group.

The intervention will be conducted after pain associated to menses begins. The information in the envelopes will contain instructions for the intervention. These will explain how to access the intervention, additionally, it will contain information on what to do while enrolled to the study. The patient will be instructed to avoid taking drugs or doing any analgesic therapy before receiving the allocated intervention. Nevertheless, it will be clarified to the patient that she can do any form of analgesia if needed but it should be informed to researchers. The intervention will be avoided if patients have to endure pain for 12 hours or more, or those that use any form of analgesia before the intervention. Both of these will be clearly instructed to participants. Patients that can't receive the interventions due to the afore-mentioned situations will not be excluded as they can receive the intervention at any other menstrual cycle.

Patients will contact the researchers for the intervention, at that moment, patient will give the coded number and researchers will identify a package to give (package A or package

¹ *[not in the original protocol] - Note: the final speech did not disclose the experimental group or the main outcome (pain) as requested by IRB for approval (communication DVN021-1-088 and approval communication DVN21-1-099-CEI856) - .*

B)¹. The researcher that gives the package will not be involved in data collection nor will have knowledge of them. The other researcher will not know which package was given to the student. After receiving the package, the other researcher will guide the patient to the place where the intervention will be conducted.

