Every package will contain an MP4 electronic device and a set of headphones. Packages will be identical and the music device will be set to look the same visually. The researcher will apply a first questionnaire to collect demographic data, medical history, surgical history, gynecologic and obstetric history, the first VAS evaluating usual pain (VAS1) in dysmenorrhea, and the first measurement of vital signs (all measurements will be collected according the explained protocol in the variables and measurement tool section). After this, another VAS evaluating acute pain (VAS2) and the short version of the Zung's anxiety scale will be collected.

The student will put on the headphones and the researcher will set the volume at 50 dB, and will play the file "AUDIO 1", and then he will leave the place. The volume is under security ranges established by Resolution 8321 of 1983 from the Ministry of Health from Colombia. This established that, the maximum level of sound intensity would be 105 dB for continuous expositions during 1 hour. The student should stay for 30 minutes listening to the AUDIO 1 file following the instructions of the package. The instructions will also explain to the patient that she can't mention what she listened through the headphones (during the intervention or even after it). Additionally, patient will be explained that she can't modify the volume during the 30 minutes. The patient is free to stop the device and the intervention but this should be informed to the investigator immediately. After the 30 minutes of the intervention the researcher will enter again the room.

After ending the intervention and entering back, the researcher will collect the following data: pain perception according to VAS (VAS3), anxiety using the Zung's scale, vital signs, and the patient will be asked if she desires to take any analgesia at that moment. Additionally, the patient will be given another questionnaire that includes: pain perception using a VAS (VAS4), anxiety using the short version of the Zung's scale, information about any drug or other form of analgesia used. This questionnaire should be answered by the student 3-6 hours after the intervention. This questionnaire should be delivered to the investigators. The patients will be able to bring with them any type of analgesic (the ones they usually used) and to initiate their usual analgesia after collection of variables post-intervention.

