Data collection:

The following figure shows the different moments for data collection:

DD, demographic data; MH, medical-surgical history; GH, gyneco-obstetric history; VAS1, usual menses pain; VS, vital signs; VAS2, pain perception before the intervention; ZS1, anxiety before the intervention; VAS3, pain perception after the intervention; ZS2, anxiety after the intervention; AR1, analgesic requirements after the intervention; VAS4, pain perception 6 hours after the intervention; ZS3, anxiety 6 hours after the intervention; AR2, used drugs or other analgesic therapies up to 6 hours after the intervention.

Sample calculation:

Considering the objectives of this study, the main endpoint is the change in pain perception evaluated with a VAS. For the sample calculation a one sided alternative hypothesis, a significance level (*p* value) α of 0.01 and a power (1- β) of 0.90 ($\beta=0.1$) was established.

The following are the null hypothesis (H_0) and alternative hypothesis (H_1):

- H_0 : no differences in the change of the acute pain perception (ΔP) in primary dysmenorrhea, from before the intervention (VAS2) until the moment after the intervention (VAS3), among the control (CG) and the experimental (MG) groups.

$$\begin{aligned} \text{VAS2}_{\text{CG}} - \text{VAS3}_{\text{CG}} &= \text{VAS2}_{\text{MG}} - \text{VAS3}_{\text{MG}} \\ \Delta P_{\text{CG}} &= \Delta P_{\text{MG}} \end{aligned}$$

- H_1 : Students listening to music (MG) will have a larger pain reduction (ΔP), from the moment before the intervention (VAS2) to the moment after (VAS3) the intervention, compared to silence group (CG).

- $VAS2_{CG}-VAS3_{CG} < VAS2_{MG}-VAS3_{MG}$
 - $\Delta P_{CG} < \Delta P_{MG}$

The prevalence of primary dysmenorrhea in the students from two programs (medicine and psychology) of the School of Medicine and Health Sciences from Universida del Rosario was described as 73%, with a mean pain intensity of 5.8 (SD 2.0) using a VAS (27). Nevertheless, no studies reporting the efficacy of music listening for pain relief in dysmenorrhea has been published, therefore there are no data regarding the change of pain intensity in the studied group. Moreover, the control group will wear headphones in silence while resting in the same conditions, this type of control (placebo) has not been described in the literature and won't allow an accurate sample calculation. Due to this, the first part of the study will be done as a pilot study for a better sample calculation.

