Nonetheless, it was decided to review data in similar context to do an initial sample calculation before the pilot. As mentioned, menses pain has been compared to labor pain, therefore, three studies evaluating this pain were review (46-48). One research compared music against massage and a VAS of 6 points was used so it was not considered (46). One study compared music against control (usual care) (47), and the other compared against Hoku point massage and a control group (usual care) (48). Both studies were done in primiparous women, and pain was measured with a 0-10 point and no additional analgesia was received until the intervention (47-48). These studies reported a mean age of 26.63 (SD 4.02) years old (47); and 21.43 (SD 2.58) years old (48). If averaged, the age of the studies is 24.03 years old, similar to the mean age of our target population 19.3 (SD 2.8) (27).

The mean pain before the intervention, measured at 4 cm of cervical dilation, was 6.43 (SD 2.57) (47), and 5.58 (SD 1.29) (48). If both means are averaged, a mean perception is 6.01, which is similar to that of the target population (27). Mean score after the music intervention during the latent phase was 4.43 (SD 1.03) with a mean difference of -1.15 that corresponds to a 20% pain reduction. For the control group the mean before the intervention was 6.13 and after was 6.48 that corresponds with a mean difference of + 0.35 (increased). Comparing both differences, the change between groups was 1.58 supporting the music group (48). The other study (47) did not report mean pain scores after the intervention, but they did report a mean difference between groups of 1.68 supporting music group. Considering these reports, a mean difference between groups of 1.5 in pain relief supporting music group was established.

The following formula was used:

$$n = ((AR+1)/1) \cdot (Z[1-\alpha]+Z[1-\beta])^2 \cdot \sigma^2 / \Delta^2$$

n= sample per group

AR (allocation rate) = 1

$Z[1-\alpha] = 2.33$

$Z[1-\beta] = 1.28$

$\sigma = 2$

$\Delta = 1.5$

According to this, n=46.34. In consequence, 47 students per group was calculated. After the pilot testing a new calculation will be done with more data obtained from the studied population and the interventions to study¹.

Data analyses

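### As the Procedure reads, usual pain (and, by inference, last-cycle analgesic use and two inclusion criteria) is first recorded at the painful session, after randomisation, although it could be taken at enrolment

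*Combined protocol and SAP*

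**What the plan says.** Section 3, Procedure, gives this order. Students are screened with a short questionnaire, hear the explanation, sign consent and are randomised. No baseline form is mentioned at that visit. They contact the researchers once menstrual pain has begun, receive a package and are taken to the room. There the researcher applies an initial questionnaire covering demographics and medical and surgical history, then "gynecologic and obstetric history, the first VAS evaluating usual pain (VAS1) in dysmenorrhea, and the first measurement of vital signs". The next sentence reads "After this, another VAS evaluating acute pain (VAS2) and the short version of the Zung's anxiety scale will be collected".

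On analgesia before the session: "The patient will be instructed to avoid taking drugs or doing any analgesic therapy before receiving the allocated intervention". The same section allows analgesia if needed. A session is avoided in any cycle in which analgesia was used or pain has lasted 12 hours or more, and the woman may be treated in another cycle.

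Supplement 2 holds demographics, history, pain onset and duration (items 2 and 3), the item "Did you take any drug for pain relief during your last menses" (item 5), non-drug strategies (item 6) and VAS1 (item 7). It carries no timing label. Supplement 4 is headed as the form for the intervention day and holds acute pain, anxiety, wish for analgesia, time in pain and vital signs.

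Section 2.2 has one objective on usual pain and another, "To describe the analgesic strategies and drugs used for pain relief in primary dysmenorrhea in the studied population".

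**The concern.** Neither usual pain nor analgesic habit depends on the session, yet as the Procedure reads both are first asked there. Four consequences follow.

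- A woman marks her usual pain while in acute, unmedicated pain, minutes before marking current pain on a similar 10 cm line. The usual-pain mark may be pulled towards the current one.
- For a woman deferred from an earlier cycle, the last menses may be one in which trial instructions about analgesia already applied. Her answer may then reflect trial conduct rather than habit.
- A randomised woman who never reaches a session supplies no usual pain, analgesic history or demographics. She is absent from both descriptive objectives, and attenders cannot be compared with non-attenders.
- Inclusion criteria 3b (pain starting no more than 24 hours before bleeding) and 3c (pain lasting 24 to 72 hours) are not asked in Supplement 1, the eligibility form. They appear only as Supplement 2 items 2 and 3. On the Procedure's sequence, these answers are recorded after randomisation.

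At stake are the accuracy and denominator of two descriptive objectives, and the point at which eligibility is documented.

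**Working it through.** **1. Timing.** Three features of the Procedure place the form at the session: enrolment is described without it; it follows the walk to the room; and it is paired with the first vital signs, which are on Supplement 4, the session-day form. Against this, Supplement 2 has no timing label and is separate from Supplement 4, and the data-collection figure is not shown. The session timing of VAS1 is therefore stated by the Procedure. That of items 2, 3, 5 and 6 is inferred from their being on the same form.

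**2. Eligibility.** Supplement 1 asks whether crampy lower-abdominal pain accompanies menses, but not when it starts or how long it lasts. Supplement 2 item 2 offers an onset of 48 to 24 hours before menses, and item 3 offers durations under 10 hours and of 10 to 24 hours. These answers can fall outside 3b and 3c. The plan does not say what happens to a randomised woman who gives one.

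**3. The plan's sample size.** Sample calculation: "For the sample calculation a one sided alternative hypothesis, a significance level" "of 0.01 and a power (1- β) of 0.90", with "a mean difference between groups of 1.5 in pain relief supporting music group was established" and σ = 2.

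n = 2 × (2.33 + 1.28)² × 2² / 1.5² = 46.34, rounded up to 47 per group. This reproduces the plan's figure. Neither VAS1 nor Supplement 2 enters it, and the primary contrast uses only VAS2 and VAS3, so moving the form leaves n at 47.

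**4. Precision of mean VAS1.** With the SD of 2.0 from the earlier survey and 94 women (2 × 47): SE = 2.0 / √94 = 0.206 cm; 95% half-width = 1.96 × 0.206 = 0.40 cm.

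**5. Pull of current pain (assumed inputs).** Shift = pull fraction × gap between current and usual pain. For a 2 cm gap and a pull of 10 to 30%: 0.10 × 2 = 0.2 cm to 0.30 × 2 = 0.6 cm. The mean shifts this far only if the gap runs the same way in most women; otherwise the shifts partly cancel.

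**6. Selection and mean VAS1 (assumed inputs).** Bias = (1 − r) × d, where r is the proportion reaching a session and d the difference in usual pain between non-attenders and attenders. With r = 0.9 and d = 0.5: 0.1 × 0.5 = 0.05 cm. With r = 0.6 and d = 1.5: 0.4 × 1.5 = 0.60 cm.

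**7. Selection and drug use (extreme case).** The earlier survey, under Background, found that 91.3% used a drug. Suppose every non-attender is a user. Attenders then show (0.913 − (1 − r)) / r:

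| Reaching a session | Drug use among attenders | Shortfall (points) |
|---|---|---|
| 90% | 90.3% | 1.0 |
| 80% | 89.1% | 2.2 |
| 70% | 87.6% | 3.7 |
| 60% | 85.5% | 5.8 |

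Women deferred because they took analgesia would answer yes to item 5, which pushes the other way. The net direction is unknown.

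**The case against.** The best defence is that the forms suggest the intended practice. Supplement 4 is the form for the day, and its pre-intervention part is just what a lean session would collect, so Supplement 2 may have been meant for enrolment. That makes the timing of the individual items uncertain. It does not override the Procedure, which puts VAS1 at the session and describes no earlier collection. If earlier completion was intended, the Procedure needs correcting.

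On the last menses, the Procedure allows analgesia if needed, and Supplement 6 advises usual treatment when the 12-hour window is missed. A deferred woman's last cycle may therefore look quite ordinary. This stands: the answer may be affected, but in an unknown direction.

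On selection, women who miss a cycle are deferred, not excluded, and waiting for one session does not show a low need for relief. The plan does not define its studied population, so describing only women who had a session is a possible reading. This limits the point to women who never attend. Nor is there a clear mechanism by which acute pain alters recall of whether a drug was taken.

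A reader might also infer that the form materially delays analgesia. The documents do not support this: no completion time is given, most items are tick-box or one-line, and analgesia is allowed if needed, although that cycle's session is then avoided.

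On eligibility, the Procedure says screening is based on the inclusion and exclusion criteria, so a researcher might ask about onset and duration aloud. No form supplied for that step records the answers.

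**Conclusion.** The point holds as a minor improvement to descriptive data and to the documentation of eligibility. As the Procedure reads, VAS1, and by inference the rest of Supplement 2, is completed after randomisation, in acute pain, and only by women who reach a session. Usual pain and analgesic history may be affected.

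A reader might conclude that both objectives are distorted by a known amount. The documents do not support that: they give no attendance rate, recall effect or gap between current and usual pain. The shifts of 0.2 to 0.6 cm (recall) and 0.05 to 0.60 cm (selection) rest wholly on assumed inputs, and the 1 to 6 point shortfall in drug use is an extreme case for 60 to 90% attendance.

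Nor does the point reach the primary result. Any carry-over from VAS1 to VAS2 comes before the intervention in both arms, so the randomised comparison of VAS2 minus VAS3 stays fair, and alpha, power and 47 per group are unchanged.

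**What to change.** Reconcile the Procedure with the supplements and state when each form is completed:

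- Have Supplement 2, including VAS1, completed at enrolment, after consent and before randomisation and the envelope. Check items 2 and 3 against criteria 3b and 3c at that point.
- At the session, collect only the pre-intervention part of Supplement 4: acute pain, anxiety, items 3 and 4, and vital signs.
- Report usual pain and analgesic strategies for all enrolled women, and say that this is the denominator.

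The cost is a few more minutes at enrolment. The women are already present, no form is added, the session is shorter, and no clinical rule or sample-size input changes.
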